### 6.5.1. Post-Treatment Active Surveillance Phase

Subjects who discontinue trial treatment in a complete remission or partial remission (mCR/mCRi/ CR/CRi/PR, see Appendix A) at the time of the safety follow-up visit will remain as a subject of this protocol but move into the Active Surveillance Phase and will be assessed every 1-3 months for up to two years (from the start of treatment) according to the NCCN consensus guidelines. This phase will continue until the start of new anti-neoplastic therapy, disease progression, death or end of the study at which point a subject would go off study and enter the post-study follow up stage.

### 6.5.2. Off Study Visit (all patients)

Subjects who meet off-study criterion listed above (Section 5.8) will be assessed in a final office study visit and referred back to his or her referring physician, consented to the Hematology Branch evaluation and treatment protocol (94-H-0010) for consideration for standard therapy or evaluated for eligibility for another branch protocol, depending on what is considered to be in the best interest of the subject. Such subjects will, where possible, enter the post-study follow-up stage (below). For those who come off study in the first eight cycles this may also serve as the safety follow-up visit (see 6.5.1 above).

### 6.5.3. Post-study follow-up stage (all patients)

After the end of treatment, each subject will be followed for 30 days for adverse event monitoring. After a subject completes the study they will be offered the opportunity to consent to an alternative hematology branch protocol (eg: 94-H-0010) to allow follow-up contact, ordinarily by telephone, approximately every 13 weeks to assess for remission and survival status until death, withdrawal of consent, or the end of the study, whichever occurs first.

## 7.0 LABORATORY RESEARCH SAMPLES

### 7.1. Collection of Research Samples

**Peripheral Blood samples:** Volume collected for clinical and research purposes will not exceed 550 ml during any 8-week period.

**Leukapheresis:** A 4-5 liter leukapheresis procedure for research may be obtained prior to initiating therapy, and/or at the completion of the study, in consenting subjects.

**Bone marrow biopsies and aspirate:** Bone marrow biopsy and up to 25 mls of BM aspirate may be obtained for research at the time of the BM biopsy as described in Section 6.3.

**Tissue for germline sequencing:** A non-invasive buccal cheek swab and/or saliva samples may be collected. A skin punch biopsy may also be collected at the end of treatment.

Please see Appendix E for time-points where research samples are anticipated to be collected. Research blood collection at each of these time points is not obligatory and may be cancelled or reduced at the discretion of the

investigator on clinical and/or research grounds. Additional research samples may be collected at time of clinical event subject to the limits described above.

## **7.2. Research Testing**

All or a selection of the following laboratory studies will be performed:

- Detection, quantification and characterization of protein, carbohydrate and/or lipid biomarkers.
- Evaluation of gene expression in unsorted and sorted biologic samples (e.g.: blood and marrow).
- Evaluation of protein expression in unsorted and sorted biologic samples.
- Evaluation of gene variants and mutations in unsorted and sorted biologic samples.
- Determination of epigenetic, histone and chromatin modifications.
- Evaluation of cellular phenotype in unsorted and sorted biologic samples.
- Evaluation of cellular function in unsorted and sorted biologic samples.
- Use of biologic samples to develop, test, and validate novel therapeutic agents.
- Use of biologic samples to develop, test, and validate surrogate predictive and prognostic markers of disease behavior.

A variety of molecular biology techniques including real-time quantitative PCR and sequencing of both DNA and RNA will be performed on research samples. Sequencing may involve single cell sanger sequencing, targeted panels, exome or genome level sequencing of sorted and unsorted biological samples (including from those enriched for tumor, and those predominantly tumor-free).

All the above laboratory studies are investigational. Studies described in Appendix D: NHLBI Hematology Branch Laboratory Research Studies may also be performed.

Sequencing results performed in a CLIA certified laboratory and ordered for a clinical indication as described in Section 6 will be returned to patients. If in the course of research analysis of whole genome/exome sequencing a gene variant of medical importance is found, the investigator will return to the IRB to discuss the next steps.

## **8.0 BIOSTATISTICAL CONSIDERATIONS**

### **8.1. Primary statistical hypothesis**

The primary statistical hypothesis is that pembrolizumab and decitabine can be co-administered safely in non-HSCT relapsed or refractory patients.

### **8.2. Sample size**

The sample size is 10 patients. This is a pilot study.

### **8.3. Statistical safety monitoring**

Given that the primary hypothesis is for feasibility, we will monitor the progress of the patients in the study. Following Geller *et. al.*, we use a Bayesian stopping rule for safety. For a given patient the safety endpoint is defined as grade 4 or 5 treatment related adverse event (excluding hematological toxicity, see section 9.1.2). This endpoint encompasses causes of death and severe toxicity from pembrolizumab and/or decitabine therapy during the induction phase (eight cycles) and, as such, is a suitable safety endpoint. Before the data are

collected, we assume that the prior distribution of the proportion of patients who will experience the safety endpoint follows a beta distribution. We combine the beta prior and the proportion data to form a beta posterior.

We anticipate the rate of treatment-related toxicities and deaths within the study period to be 50% or less. Since the proportion is a realization of a beta distribution, the proportion parameter is not a fixed quantity but a random variable. We assume the prior mean to be 0.3, and our prior knowledge is “worth” two patients. The conditions are satisfied where we set  $a=0.6$  and  $b=1.4$  for the beta distribution. Note that  $a+b$  is interpreted as the measure of contribution of the prior distribution. The subjective contribution of two patients, added to the sample of ten patients, is quite modest and does not exert undue influence on the data characteristics.

We set the stopping boundary for the event that the posterior probability, given accruing data, exceeds 0.8 when the posterior proportion of the specified events is greater than 0.5. That is,  $\text{Prob}(p>0.5|\text{data})>0.8$ . The resulting boundaries are shown in the Table 8 below.

No. Patients	Stop if toxicities reaches or exceeds	Posterior Probability
3	3	0.86
5	4	0.81
7	5	0.78
8	6	0.86
10	7	0.83

We evaluated the performance of this stopping rule with computer simulations. In each simulation we generated a study with 10 independent Bernoulli trials, each with prior proportion  $p$  for having toxicity and compared the outcome with the stopping boundary. We repeated the simulation 100,000 times and counted the number of times the study was stopped. We did this for a number of different prior proportions to investigate whether our benchmark of 0.5 is appropriate (Table 9 below).

Proportion of SAE= $p$	0.2	0.35	0.5	0.65	0.8
Proportion of Stopped Studies	1.36%	9.74%	31.77%	64.73%	92.33%
Average number of subjects	9.92	9.49	8.44	6.76	4.83
Average number toxicities	1.99	3.33	4.22	4.39	3.86

These results suggest our stopping rule has a low probability of stopping a study when the proportion of toxicities is below the benchmark value of 50% toxicities is high when above this cut off.

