### **2.5.2. Decitabine**

Decitabine was studied in 3 single-arm studies (N=66, N=98, N=99) and 1 controlled supportive care study (N=83 decitabine, N=81 supportive care). The data described below reflect exposure to decitabine in 83 patients in the MDS trial. In the trial, patients received 15 mg/m^2 intravenously every 8 hours for 3 days every 6 weeks. The median number of decitabine cycles was 3 (range 0 to 9).

*Most Commonly Occurring Adverse Reactions:* neutropenia, thrombocytopenia, anemia, fatigue, pyrexia, nausea, cough, petechiae, constipation, diarrhea, and hyperglycemia.

*Adverse Reactions Most Frequently ( $\geq 1\%$ ) Resulting in Clinical Intervention in the Phase 3 Trials in the decitabine Arm:*

Discontinuation: thrombocytopenia, neutropenia, pneumonia, Mycobacterium avium complex infection, cardio-respiratory arrest, increased blood bilirubin, intracranial hemorrhage, abnormal liver function tests.

Dose Delayed: neutropenia, pulmonary edema, atrial fibrillation, central line infection, febrile neutropenia.

Dose Reduced: neutropenia, thrombocytopenia, anemia, lethargy, edema, tachycardia, depression, pharyngitis.

In the controlled trial using decitabine dosed at 15 mg/m^2, administered by continuous intravenous infusion over 3 hours repeated every 8 hours for 3 days, the highest incidence of Grade 3 or Grade 4 adverse events in the decitabine arm were neutropenia (87%), thrombocytopenia (85%), febrile neutropenia (23%) and leukopenia (22%). Bone marrow suppression was the most frequent cause of dose reduction, delay and discontinuation. Six patients had fatal events associated with their underlying disease and myelosuppression (anemia, neutropenia, and thrombocytopenia) that were considered at least possibly related to drug treatment. Of the 83 decitabine-treated patients, 8 permanently discontinued therapy for adverse events; compared to 1 of 81 patients in the supportive care arm.

In a single-arm phase 1 study of patients with hematological malignancies (N=48) decitabine was dosed at 5, 10, 15 or 20mg/m^2 daily intravenously over one hour for 10 days (5 days on, 2 days off, 5 days on), approximately every six weeks. 73% of these patients had AML and 14% had MDS. The treatment was well tolerated overall. Nonhematopoietic side effects are detailed in Table 2 below. Asymptomatic but severe

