### 9.1.2. Severity

The descriptions and grading scales found in the revised NCI Common Terminology Criteria for Adverse Events (CTCAE) version 4.03 will be utilized for grading the *severity* (intensity) of **non-hematologic** AEs (<http://ctep.cancer.gov/reporting/ctc.html>).

Given the pathobiology of Acute Myeloid Leukemia, severe blood count abnormalities (up to grade 4 levels in leukocytes, neutrophils, lymphocytes, red blood cells and platelets) are expected and may be present at baseline. Thus we will record these values in the protocol database, but will not report these abnormalities as adverse or serious adverse events unless the grade of toxicity (based on NCI-Common Terminology Criteria for Adverse Events, CTCAE v4.0) is grade 4 or above and was not present at baseline. If the myelosuppressive event is fatal (Grade 5), or if the Investigator finds the event to be medically important, then it will be collected as an SAE.

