## APPENDIX C: Events of Clinical Interest

Pneumonitis (reported as ECI if <math>\geq</math> Grade 2)		
Acute interstitial pneumonitis	Interstitial lung disease	Pneumonitis
Colitis (reported as ECI if <math>\geq</math> Grade 2 or any grade resulting in dose modification or use of systemic steroids to treat the AE)		
Intestinal Obstruction	Colitis	Colitis microscopic
Enterocolitis	Enterocolitis hemorrhagic	Gastrointestinal perforation
Necrotizing colitis	Diarrhea	
Endocrine (reported as ECI if <math>\geq</math> Grade 3 or <math>\geq</math> Grade 2 and resulting in dose modification or use of systemic steroids to treat the AE)		
Adrenal Insufficiency	Hyperthyroidism	Hypophysitis
Hypopituitarism	Hypothyroidism	Thyroid disorder
Thyroiditis	Hyperglycemia, if $\geq$ Grade 3 and associated with ketosis or metabolic acidosis (DKA)	
Endocrine (reported as ECI)		
Type 1 diabetes mellitus (if new onset)		
Hematologic (reported as ECI if <math>\geq</math> Grade 3 or any grade resulting in dose modification or use of systemic steroids to treat the AE)		
Autoimmune hemolytic anemia	Aplastic anemia	Thrombotic Thrombocytopenic Purpura (TTP)
Idiopathic (or immune) Thrombocytopenia Purpura (ITP)	Disseminated Intravascular Coagulation (DIC)	Haemolytic Uraemic Syndrome (HUS)
Any Grade 4 anemia regardless of underlying mechanism		
Hepatic (reported as ECI if <math>\geq</math> Grade 2, or any grade resulting in dose modification or use of systemic steroids to treat the AE)		
Hepatitis	Autoimmune hepatitis	Transaminase elevations (ALT and/or AST)
Infusion Reactions (reported as ECI for any grade)		
Allergic reaction	Anaphylaxis	Cytokine release syndrome
Serum sickness	Infusion reactions	Infusion-like reactions
Neurologic (reported as ECI for any grade)		
Autoimmune neuropathy	Guillain-Barre syndrome	Demyelinating polyneuropathy
Myasthenic syndrome		
Ocular (report as ECI if <math>\geq</math> Grade 2 or any grade resulting in dose modification or use of systemic steroids to treat the AE)		
Uveitis	Iritis	
Renal (reported as ECI if <math>\geq</math> Grade 2)		
Nephritis	Nephritis autoimmune	Renal Failure
Renal failure acute	Creatinine elevations (report as ECI if $\geq$ Grade 3 or any grade resulting in dose modification or use of systemic steroids to treat the AE)	
Skin (reported as ECI for any grade)		
Dermatitis exfoliative	Erythema multiforme	Stevens-Johnson syndrome
Toxic epidermal necrolysis		

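### Section 8.3 leaves open whether fatal or immune-mediated hematologic events count toward the safety stopping boundary, while stating that the endpoint covers causes of death

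*Combined protocol and SAP*

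**What the plan says.** Section 8.3 applies a Bayesian boundary to one binary endpoint per patient: "grade 4 or 5 treatment related adverse event (excluding hematological toxicity, see section 9.1.2"). The exclusion carries no exception for grade 5. The next sentence states: "This endpoint encompasses causes of death and severe toxicity from pembrolizumab and/or decitabine therapy", for the eight induction cycles, and on that ground calls the endpoint suitable. The same section sets its 50% benchmark for toxicities and deaths together.

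Section 9.1.2 gives the reason for treating blood counts separately: "severe blood count abnormalities (up to grade 4 levels in leukocytes, neutrophils, lymphocytes, red blood cells and platelets) are expected and may be present at" the outset. Such values go into the database but are not reported as adverse events unless the grade "is grade 4 or above and was not present at baseline". It then adds: "If the myelosuppressive event is fatal (Grade 5), or if the Investigator finds the event to be medically important", the event is collected as an SAE. Nothing there refers to the stopping endpoint.

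Two other places bear on the point. Section 2.5.2, on 83 decitabine-treated patients in an MDS trial, reports: "Six patients had fatal events associated with their underlying disease and myelosuppression"; these were judged at least possibly drug related. The hematologic group in Appendix C includes "Autoimmune hemolytic anemia", aplastic anemia, TTP, ITP, DIC, HUS and any grade 4 anemia. Section 11.2.1 also places a drug-related grade 3 immune hemolysis with pembrolizumab under its hematologic heading.

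**The concern.** Taken literally, adjacent sentences of 8.3 cannot both be true. A treatment-related death from marrow failure is a cause of death from therapy, and it is also hematological toxicity, so it is claimed as covered and excluded at once. The rationale in 9.1.2 reaches only low counts that are expected in AML. It does not reach deaths, and it does not mention immune hemolysis, TTP or HUS.

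Section 8.1 makes safe co-administration the primary hypothesis. The 8.3 boundary is the only quantitative test of it, and Section 5.11 refers to Section 8.0 for the stopping calculations. If the endpoint can be read two ways, two people with the same data can reach opposite stopping decisions, and a favourable count in the final report could leave out treatment-related deaths.

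**Working it through.** **Reproducing the plan's figures.** The inputs from 8.3 are a Beta(0.6, 1.4) prior (mean 0.3, worth two patients), n = 10, and stopping when Prob(p > 0.5 | data) > 0.8. After r events in n patients the posterior is Beta(0.6 + r, 1.4 + n − r). Its upper tail at 0.5 for the printed boundaries is:

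| Boundary | 3 of 3 | 4 of 5 | 5 of 7 | 6 of 8 | 7 of 10 |
|---|---|---|---|---|---|
| Printed | 0.86 | 0.81 | 0.78 | 0.86 | 0.83 |
| Recomputed | 0.864 | 0.814 | 0.780 | 0.857 | 0.832 |
| If one of the r events is not counted | 0.54 | 0.53 | 0.53 | 0.65 | 0.64 |

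An exact patient-by-patient binomial recursion with these boundaries gives stopping probabilities of 1.39%, 9.71%, 31.64%, 64.88% and 92.27% at p = 0.2, 0.35, 0.5, 0.65 and 0.8. Table 9 prints 1.36%, 9.74%, 31.77%, 64.73% and 92.33%, so the match is within simulation error. Neither table depends on what is called an event. Only the data fed into them change.

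**What turns on the definition.** Suppose the first three patients all have fatal treatment-related hematologic events and nothing else.
- Counted: r = 3, posterior Beta(3.6, 1.4), probability 0.86, stop.
- Not counted: r = 0, posterior Beta(0.6, 4.4), probability 0.02, continue.

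The last row of the table shows that one uncounted event is enough to miss any of the five boundaries.

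**Illustrative size.** The documents give no rate of fatal hematologic events for this regimen. I assume a rate h among patients without another counted event, with h = 6/83 = 7.2% (Section 2.5.2) as one value and 10% and 20% to show a range. With q the rate of events counted under the literal reading, the rate with these deaths included is 1 − (1 − q)(1 − h). For h = 7.2%:
- q = 0.30 (the prior mean): 1 − 0.70 × 0.9277 = 0.351
- q = 0.50 (the benchmark): 1 − 0.50 × 0.9277 = 0.536

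Stopping probabilities under the printed boundaries:

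| q | Deaths not counted | h = 7.2% | h = 10% | h = 20% |
|---|---|---|---|---|
| 0.30 | 5.7% | 9.8% | 11.8% | 21.0% |
| 0.50 | 31.6% | 39.0% | 42.1% | 53.4% |

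At h = 7.2% and q = 0.50, the per-patient chance of a death that the literal reading leaves out is 0.50 × 0.0723 = 0.036. The chance of at least one such death in ten patients is then 1 − (1 − 0.036)^10 = 31%.

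**A note on the boundary used.** The printed 5-of-7 boundary has posterior 0.78, below the plan's own 0.8 criterion. That is a separate matter. I kept it because Table 9 reproduces best with it. With 6 of 7 instead, the h = 7.2% contrasts are 5.0% to 8.6% and 29.0% to 36.2%.

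**The case against.** The tempting stronger reading is that 8.3 excludes all hematological toxicity, so fatal marrow failure and immune hemolysis certainly would not count. The documents do not support that certainty.
- The exclusion points to 9.1.2, which concerns expected counts up to grade 4 and treats the fatal case separately. The sentence about causes of death and the benchmark for toxicities and deaths can both be taken as evidence that grade 5 was meant to count.
- Section 9.1.2 does not name immune hemolysis, TTP or HUS, so it is not established that the exclusion reaches them. The one immune hemolysis reported was grade 3, below the endpoint's threshold on any definition.
- A death coded as infection or bleeding and judged treatment related counts under either reading.
- There are backstops. Section 5.11 has a general adverse-reaction criterion, the DSMB sees related AEs and SAEs and may recommend termination, hematologic events of clinical interest go to the sponsor within 24 hours, and the feasibility outcome in Table 7 is a descriptive summary of all adverse events.

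A reader might also infer a 53% chance of at least one uncounted death, from 1 − (1 − 0.0723)^10. That ignores patients already counted for another event; the figure is 31% at a 50% counted rate. The 6/83 itself comes from MDS patients on 15 mg/m² every 8 hours for 3 days and mixes disease and drug causes. Not all six deaths need have been coded as hematologic.

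These points make the defect an ambiguity, but they do not remove it. Section 9.1.2 is a reporting rule and never says what 8.3 counts. The backstops rest on judgment, and the DSMB meets only every six or twelve months. A pre-specified endpoint should not depend on inferred intent.

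**Conclusion.** The point holds as an unresolved conflict between 8.3 and 9.1.2. As written, the documents do not say whether a fatal treatment-related hematologic event, or a grade 4–5 immune-mediated one, counts toward the boundary. The literal wording of 8.3 excludes the fatal event while claiming to cover it.

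The effect on average operating characteristics is modest: about 4 percentage points of stopping probability at a 30% counted rate and about 7 at 50%. This rests on a borrowed 7.2% rate, independence from other events and the printed boundaries, so it shows scale and does not predict. In an individual trial the effect can be decisive, as the contrast of 0.86 with 0.02 shows. No rate is available for the immune-mediated events, so no size is given for them.

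Section 11.3 records that accrual closed on November 30, 2017 and that from March 15, 2019 the study is in data analysis only. The boundary can no longer act on enrollment. What remains at stake is how the endpoint is counted and what the report claims for it.

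**What to change.** In 8.3, limit the exclusion to non-fatal blood count abnormalities as described in 9.1.2. State that every grade 5 treatment-related event counts, and that grade 4–5 immune-mediated hematologic events listed in Appendix C are not covered by the exclusion. Name those events, because the Appendix C hematologic group also contains DIC and any grade 4 anemia whatever its mechanism, and the latter overlaps with the counts that 9.1.2 sets aside. Add a line to 9.1.2 pointing back to 8.3.

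In the analysis, report the number of patients meeting the endpoint on this definition. Label it as a clarification made after accrual closed, and give the literal count beside it so that the reader can see whether any patient changes status. If the sponsor prefers to keep the broad exclusion, withdraw the statement that the endpoint covers causes of death and disclose what is left out.

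The cost is a few sentences and a re-check of at most 15 patients (the maximum accrual). Tables 8 and 9 do not change arithmetically. The downside is a slightly higher counted rate judged against a prior mean of 0.3 and a benchmark of 0.5 that were set for the endpoint as specified, so the sponsor should confirm that both still fit the clarified one.

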**Subjects of Study:**

Number	Sex	Age-range
10	M/F	18-99

(Maximal accrual including replacement subjects: 15)

Ionizing Radiation for Research:	No
Off-Site Project:	No
Multi-center trial:	No
DSMB Involvement:	Yes
Tech Transfer:	Yes
IND:	Yes (IND number 131826)

Version: 11.0

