### **5.10. Subject Replacement Strategy**

If a patient discontinues treatment prior to receiving fourth dose of Pembrolizumab, due to patient or investigator action/decision, that patient may be replaced with another subject. Maximum accrual will be fifteen subjects.

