### **11.3. Risks in Relation to Benefit**

Relapsed and refractory Acute Myeloid Leukemia is fatal without treatment. Even with the best available treatment it is fatal in the majority of cases. The benefits to the adult patient on this study could be a control, reduction or elimination of detectable AML potentially resulting in an improved quality of life, decreased transfusion requirements, a decreased susceptibility to infections, become eligible to receive additional therapy such as allogeneic transplant and foremost a significant improvement in survival time. Potentially, treatment with other therapies could also be avoided or postponed.

As of November 30, 2017 this study was closed to new subject accrual and in subject follow up only. As of March 15, 2019, the study will continue in data analysis only and the level of risk is minimal.

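### Table 8 stops at 5 toxicities in 7 patients, where the posterior is 0.78 and so below the stated 0.8 threshold; Table 9 describes the printed boundary, not the stated rule

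*Combined protocol and SAP*

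**What the plan says.** Section 8.3 monitors the proportion p of patients who have a treatment-related event of grade 4 or 5 during induction, haematological toxicity excluded. On the prior it says: "We assume the prior mean to be 0.3, and our prior knowledge is “worth” two patients". A beta distribution with a = 0.6 and b = 1.4 is chosen to match. The rule reads: "We set the stopping boundary for the event that the posterior probability, given accruing data, exceeds 0.8 when the posterior proportion". The benchmark for p is 0.5. The section then writes this as Prob(p>0.5 | data) > 0.8 and gives Table 8 as its result:

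| Patients | Stop at | Posterior printed |
|---|---|---|
| 3 | 3 | 0.86 |
| 5 | 4 | 0.81 |
| 7 | 5 | 0.78 |
| 8 | 6 | 0.86 |
| 10 | 7 | 0.83 |

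Table 9 reports 100,000 simulated 10-patient studies compared with the boundary at p = 0.2, 0.35, 0.5, 0.65 and 0.8: "Proportion of Stopped Studies 1.36% 9.74% 31.77% 64.73% 92.33" (per cent), together with average numbers of subjects and toxicities.

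Two other places bear on the point. Section 11.3 records: "As of November 30, 2017 this study was closed to new subject accrual and in subject follow up only". The Subjects of Study listing has "Maximal accrual including replacement subjects: 15", and Section 5.10 repeats "Maximum accrual will be fifteen subjects".

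**The concern.** The row for 7 patients contradicts the rule it is said to come from, and the contradiction is visible on the page, because 0.78 does not exceed 0.8. This is the only numerical stopping boundary in the protocol, and Section 5.11 refers early termination to it. With 5 toxicities among 7 patients, a reader of the text continues and a reader of the table stops. If Table 9 was computed from the table rather than from the text, the operating characteristics shown to the monitoring board and the IRB are not those of the stated rule.

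**Working it through.** **Inputs (all from Section 8.3).** Prior Beta(a = 0.6, b = 1.4), which gives mean 0.6/2.0 = 0.3 and weight a + b = 2, as stated. Benchmark 0.5, threshold 0.8, 10 patients, 100,000 simulations.

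**Step 1: Table 8 posteriors.** With x events in n patients, Prob(p>0.5 | data) = 1 − BetaCDF(0.5; 0.6 + x, 1.4 + n − x).

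| x/n | Computed | Printed | Above 0.8? |
|---|---|---|---|
| 3/3 | 0.8636 | 0.86 | yes |
| 4/5 | 0.8140 | 0.81 | yes |
| 5/7 | 0.7803 | 0.78 | **no** |
| 6/8 | 0.8569 | 0.86 | yes |
| 7/10 | 0.8323 | 0.83 | yes |

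Every printed posterior is right, so 0.78 is not a misprint; the row itself fails the rule. At n = 7 the rule is first met by 6 events (0.9335). Rounding 0.78 up to 0.8 does not explain the row, because 6/9 (0.7555) would then also round to 0.8 and stop, and Table 8 has no such row. The printed rows correspond to a cut-off between about 0.756 and 0.780.

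**Step 2: which rows can act.** If 5/7 stops, the 6/8 row can never act, because 6 events in 8 patients means at least 5 in the first 7. Under >0.8 the 6/8 row can act, and the 7-patient entry (6) can never be reached first, because 6/7 means at least 4/5. Checking after every patient or only at the listed n gives the same results under either boundary.

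**Step 3: operating characteristics.** Exact enumeration of all event paths, N = 10, stopping at the boundary. The simulation standard error (SE) is sqrt(q(1−q)/100,000), with q from Table 9: 0.04, 0.09, 0.15, 0.15 and 0.08 percentage points.

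| p | 0.2 | 0.35 | 0.5 | 0.65 | 0.8 |
|---|---|---|---|---|---|
| % stopped, Table 9 | 1.36 | 9.74 | 31.77 | 64.73 | 92.33 |
| % stopped, printed boundary | 1.39 | 9.71 | 31.64 | 64.88 | 92.27 |
| % stopped, stated rule | 1.25 | 8.57 | 29.00 | 62.30 | 91.42 |
| Subjects, Table 9 | 9.92 | 9.49 | 8.44 | 6.76 | 4.83 |
| Subjects, stated rule | 9.92 | 9.54 | 8.59 | 6.97 | 5.00 |
| Toxicities, Table 9 | 1.99 | 3.33 | 4.22 | 4.39 | 3.86 |
| Toxicities, stated rule | 1.98 | 3.34 | 4.29 | 4.53 | 4.00 |

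Table 9 lies within about 1 SE of the printed boundary throughout, and about 3, 12, 19, 16 and 11 SEs from the stated rule. It was therefore computed from the printed boundary.

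**Step 4: hand check of the difference.** The two rules part only at 5/7 with no earlier stop. That needs 3 events in the first 5 patients, not all in the first 3 (10 − 1 = 9 orderings), followed by two events: probability 9p^5(1−p)^2. At the five values of p this is 0.2, 2.0, 7.0, 12.8 and 11.8%. From there the stated rule still stops later if patient 8 has an event, or if patients 9 and 10 both do. It fails to stop with probability (1−p)(1−p^2). At p = 0.5: 9/128 = 7.03%, times 0.5 × 0.75 = 0.375, gives 2.64 points, which equals 31.64 − 29.00. Across the five values the differences are 0.14, 1.14, 2.64, 2.59 and 0.85 points.

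**Step 5: beyond 10 patients (secondary).** Both tables end at 10, although accrual may reach 15. If all 15 count in the monitoring denominator, the entries for n = 11 to 15 are 8, 8, 9, 10, 10 under >0.8, with 9.3, 33.8 and 72.3% stopped at p = 0.35, 0.5 and 0.65. Under >0.78 they are 8, 8, 9, 9, 10, with 10.6, 37.2 and 75.3% stopped. The two rules differ again at n = 14, where 9/14 has posterior 0.7951.

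**The case against.** The best defence is that Table 8 is an explicit instruction, prints 0.78 openly, and is what Table 9 simulates. Two of the three elements agree, so the threshold sentence looks like the slip. That is a fair inference about what may have been used, but it does not settle the matter: the text derives Table 8 from the 0.8 threshold and gives no exception or second cut-off for 7 patients.

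The practical objections stand and limit the weight of the point. Only one configuration is affected, the stopping probability moves by at most 2.64 points, the printed row errs toward stopping earlier, accrual has ended, and nothing in the documents says that 5 of 7 was approached.

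The row that cannot act is redundant rather than contradictory, and either rule leaves one such row, so it does not tell the two rules apart.

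The 15-patient figures depend on replaced patients staying in the denominator. The documents do not say whether they do. If monitoring covers 10 patients net of replacements, that part falls away.

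**Conclusion.** The concern holds. The text and Table 8 give opposite decisions at 5 toxicities in 7 patients (posterior 0.7803 against a threshold of 0.8), and Table 9 gives the operating characteristics of the printed boundary rather than of the stated rule. Taking the stated rule at its word, Table 9 overstates the stopping probability by 0.14 to 2.64 points (exact against exact), and the average number of subjects is up to 0.21 too low (6.76 against 6.97 at p = 0.65). The calculations assume independent patients with a common p and 10 monitored patients, as the protocol's own simulation does. The documents do not show which boundary was in force. With the study in data analysis only since March 15, 2019 (Section 11.3), the error can no longer affect a stopping decision. It does affect what is reported as the pre-specified rule and whether that rule was met, so it should be corrected.

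**What to change.** State which rule was actually applied, and bring text and tables to that one rule.

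- **If it was >0.8:** change the 7-patient entry to 6 (posterior 0.93), or delete the row because it can never be reached first. Replace the three result rows of Table 9 with the stated-rule figures above.
- **If it was the printed boundary:** restate the threshold as >0.78 (any cut-off between 0.756 and 0.780 gives the same rows) and leave Table 9 as it stands for 10 patients.

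In either case, say whether replacement patients count in the monitoring denominator. If they do, extend Table 8 to 15 patients with the entries that follow from the chosen threshold.

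The edit is one table row or one number in the threshold sentence, plus three rows of Table 9 in the first case. It needs no new data and changes nothing for patients or procedures. A formal amendment would need Merck's approval and then IRB approval under Section 9.7. As accrual is closed, a clear statement in the final report of the boundary applied and its operating characteristics would serve the same purpose.
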